1.0 Introduction and Background

The Centers for Disease Control (CDC) estimates 1.9% of the estimated 16 million surgical procedures each year in the United States are complicated by a surgical site infection (SSI). The overall incidence of SSI with hysterectomy is between 1-2 %. [1,2]

Surgical site infections are classified as follows:

A 2011 study of postoperative surgical patients (general and vascular surgery) identified that SSI resulted in \$10,000 of excess hospital costs and prolonged hospital stay. [3] **In endometrial cancer patients, SSIs accounted for a \$5447 median increase in the 30-day cost of care.[4]** A recent article in AJOG 2017 noted SSI rates of 2% associated with hysterectomy with an added cost of \$5000 per case. [5] **Approximately 2/3 of gynecologic SSI are superficial incisional infections.[6]**

The Centers for Disease Control developed a Surgical Wound Classification system as outlined. This designed as a risk model for (SSI). As noted with an increase in the class there is an increase in the potential for infection.

Secondary versus Tertiary Wound Closure in High Risk
Gynecologic Abdominal Surgical Incisions
CCCWU # 04418

Surgical Wound Classification

Wound Class	Definition	Examples	Reminders
Class I Clean	
 ► Operative wound clean ► Non-traumatic, with no inflammation encountered ► No break in technique ► Respiratory, gastrointestinal and genito-urinary tracts not entered ► Caesarean Section, elective, no pre-rupture of membranes or trial of labor 	
 ► Vascular Procedures ► Neurological procedures (inflamed II, infected III) ► Endocrine procedures ► Eye surgery (inflamed II, foreign body III, infected III) ► Orthopedic procedures (unless: trauma III, old wound IV, inflammation II) ► Penile prosthesis ► Skin (mastectomy, lumpectomy, lesions, lipoma, cosmetic, I&D IV, old wounds III, inflamed III, infected IV) ► Exploratory Lap (no bowel involvement II) ► Miscellaneous procedures (lymph node excision/Bx unless inflamed III or infected IV, splenectomy, tenckhoff cath unless replacement II) 	
Class II Clean - contaminated	
 ► Operative wound clean-contaminated ► Non-traumatic wound with minor break in technique ► Gastrointestinal, respiratory or genito-urinary tracts entered without significant spillage ► Incisional: 
 ◦ Transection of appendix or cholecystic duct in the absence of infected bile or urine ◦ Hysterectomy ◦ Caesarean Section, emergency involving pre-rupture of membranes and / or trial of labor 	
 ► Thoracic procedures (except mediastinoscopy I, inflammation III, infected IV, foreign body III) ► GI procedures (including: laparoscopy, colonoscopy, gastroscopy) (gross spillage III, acute inflammation III, foreign body III, old wound II) (itis III, Lithiasis II) ► GU procedures (infected III) ► Ear surgery (infected III) ► Nose/Oropharynx procedures (infected IV) ► GYN procedures (Oophorectomy I, inflamed III, infected IV) 	
 ► Any wound open for drainage II (except total hip / knee) ► Removing old implants (wires, pins, etc...) ► Re-operation at the same site
Class III contaminated	
 ► Operative wound contaminated ► Fresh traumatic wound from clean source ► Operative wound with a major break in technique ► Gross spillage from the gastrointestinal tract ► Entrance into the genito-urinary or biliary tracts ► When infected urine or bile is present ► Incision encountering acute non-purulent inflammation. 	
 ► Inflammation ► Gross spillage ► Fresh accidental wound 	
 ► Foreign bodies in a wound (bullets, etc...)
Class IV Dirty - infected	
 ► Operative wound dirty ► Spillage from dirty source ► Traumatic wound with delayed treatment ► Fecal contamination ► Foreign body ► Retained devitalized tissue ► Operative wound w/ acute bacterial inflammation or perforated viscus ► Operative wound where clean tissue is transected to gain access to a collection of pus 	
 ► Infected ► I&D abscess ► Wound debridement 	
Unclassified	
 ► When unable to classify accurately an operative wound 		
 ► Communicable disease (aids, hepatitis, TB) is not classified the surgical wound is what is being classified

Classification of Surgical Wounds			
Category	Criteria	Infection rate	
Clean	No hollow viscus entered Primary wound closure No inflammation No breaks in aseptic tech Elective procedure	1 – 3%	
Clean contaminated	Hollow viscus entered but controlled No inflammation Primary wound closure Minor breaks in aseptic tech Bowel prep preop	5-6%	
Contaminated	Uncontrolled spillage from viscus Inflammation apparent Open,traumatic wound Major break in aseptic tech	20 – 25%	
Dirty	Untreated, uncontrolled spillage Pus in op wound Open suppurative wound Severe inflammation	30 – 40%	

Specifically related to gynecologic surgery, hysterectomy would be a clean contaminated or class II wound. Gross spillage from the gastrointestinal tract would be considered a contaminated or class III wound. A perforated viscus or abscess requiring surgery would be considered a dirty/infected or class IV wound. Prophylactic antibiotics are indicated for class II and III wounds; therapeutic antibiotics are necessary for class IV wounds.

Within the group of class II wounds (hysterectomy), there are a subset of patients in which there are factors that increase the risk of SSI above baseline. These include:

- a. Hyperglycemia,
- b. Smoking,
- c. Obesity (BMI \geq 30),
- d. Depth of subcutaneous tissue \geq 3 cm,
- e. Coexistent infection at a remote body site,
- f. Vaginal colonization (bacterial vaginosis),
- g. ASA status > 2,
- h. Immunodeficiency (chronic steroids, chemotherapy), and
- i. MRSA.

Numerous measures have been proved and/or recommended to decrease postoperative infection.

1. Preoperative Measures

- a. Treat remote infections
- b. Clippers if shaving needed
- c. Serum glucose control < 200 mg/dl
- d. Antimicrobial bath/shower
- e. Chlorhexidine abdominal/vaginal prep (70%/4%)
- f. Antibiotic prophylaxis

2. Intraoperative Measures

- a. Surgical technique
- b. Preventing hypothermia
- c. Appropriate re-dosing of prophylactic antibiotics
- d. Prevention of dead space and incisional seromas

Wound management techniques after fascial closure to address reduction in incisional infections especially in high risk class II and class III/IV wounds have included the following:

- Primary closure with subcutaneous drains and possibly incisional vacuum assisted closure device (VAC) for 3-4 days,
- Secondary closure with wound packing and dressing changes 2-3 times daily or VAC placement with changes 2-3 times weekly, and
- Tertiary or delayed primary closure.

Three techniques of wound treatment

- Primary intention- all tissue including skin are closed with suture material.
- Secondary intention – in which wound is left open and close naturally.
- Tertiary intention – in which wound is left open for number of days and then closed if it found to be clean.

The **vacuum-assisted closure (VAC)** as noted above involves placement of a sterile sponge with negative continuous pressure proven to remove tissue fluid, increase blood supply and stimulate the wound thus decreasing time to healing. [6,7]

Also, ETHICON has developed suture impregnated with TRICLOSAN as an antimicrobial proven to reduce some surgically related infections.

- CDC Guidelines for the Prevention of Surgical Site Infections 2017
 - Consider the use of triclosan-coated sutures for the prevention of SSI. [8]
- WHO Global Guidelines for The Prevention of Surgical Site Infection
 - The panel suggests the use of triclosan coated sutures for the purpose of reducing the risk of SSI, independent of type of surgery. [9]
- American College of Surgeons Surgical Infection Society
- The use of triclosan coated suture is recommended for wound closure in clean and clean contaminated cases when available. [10]

Abstract

Introduction

Surgical site infections (SSI) following gynecological abdominal surgeries are associated with prolonged wound healing, additional procedural costs and a lower quality of life. The purpose of this study is to describe an alternative wound closure

technique (tertiary closure) aimed at improving wound morbidity for high-risk patients compared to healing by secondary intention.

Methods

Patients undergoing surgery at high-risk (class III or III wound) for developing SSI were enrolled. Tertiary closure was performed by: 1) running a subcuticular absorbable monofilament suture with looping of the suture every 8-10 cm through the skin secured with hemoclips and by 2) placing a vacuum assisted closure (VAC) over the incision. On post-operative day four (POD #4), the incision was re-approximated at the bedside by removing the VAC and applying traction on the suture using hemoclips.

Results

Six consecutive patients undergoing gynecologic abdominal surgery had tertiary closure. The mean patient age and BMI were 51 and 28, respectively. Two patients had surgery for benign conditions and four for malignancy. Two of the six wounds were class IV (abscess) and the other four wounds were class III (GI contamination). The mean operative duration was 5.5 hours and the median length of stay was 4 days. At sixty days, no SSI or other wound complications were identified.

Conclusions

Tertiary closure of high-risk gynecological abdominal wounds is safe and feasible. Based on this data, we have designed a larger trial comparing outcomes of tertiary closure to secondary closure for high-risk patients undergoing gynecologic abdominal surgery.

2.0 Objectives

2.1 Primary Objective

2.1.1 To compare the percentage of patients whose wound remained closed on postoperative day #30 after tertiary closure compared to historical controls who underwent secondary wound closure. We are primarily looking at time to wound closure. We will be able to abstract this information from the postoperative clinic visit notes from patients in the "historical control" cohort. We will identify 20 patients with characteristics described in the inclusion criteria of this study who underwent laparotomy with secondary wound closure during the calendar year 2018.

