6.0 Analytic Plan

6.1 Sample Size and Power

Twenty patients with a tertiary closure will be recruited (experimental group). The proportion of wound closure within 30 days for these patients will be compared to the proportion from 100 historical controls receiving a secondary wound closure. We anticipate closer to 100% of wound closure in the experimental group and closer to 0% of wound closure in the control group. Assuming the significance level at 0.05 and a two-sided test, we have greater than 90% power to claim that the proportions of wound closure within 30 days are different between the two groups.

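### No rule says which historical controls are taken if more qualify than needed, and nothing keeps eligibility decisions apart from outcomes already in the chart

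*Combined protocol and SAP*

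**What the plan says.** Section 2.1.1 is the only description of how controls are obtained. It gives a number and an eligibility standard ("We will identify 20 patients with characteristics described in the inclusion criteria of this study") and a source: patients "who underwent laparotomy with secondary wound closure during the calendar year 2018". For wound closure it adds: "We will be able to abstract this information from the postoperative clinic visit notes".

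Section 6.1 gives a different number. The 20 tertiary patients are to be "compared to the proportion from 100 historical controls receiving a secondary wound closure". It also states the expected control result: "closer to 0% of wound closure in the control group".

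Sections 2.2, 5.2 and 6.4 use the historical controls for infection, length of stay and return within 30 days as well. Quality of life is described in the tertiary group only. Section 6.3 specifies a chi-squared test, with logistic regression where confounders are adjusted for; age is the only one it names. Section 6.4 carries the same approach to infection and return.

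No section states a consecutive, random, all-eligible or matched rule for the controls. None provides a screening log, a list fixed in advance, or eligibility review by someone who has not seen the outcome. The pilot abstract in section 1.0 does describe its own six patients as consecutive.

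**The concern.** The comparison is not randomised, so the way controls enter it is a main route for bias. Patients operated on in 2018 already have their healing recorded and, by inference, their infections, discharge dates and returns too. If more of them qualify than the plan takes, someone has to choose, and the plan does not separate that choice from knowledge of the outcome. Preference need not be deliberate: a chart with a well-documented wound problem is easier to find and to recognise as a secondary-closure case.

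Adjustment for age or similar baseline factors does not repair this. Regression can balance measured baseline differences; it cannot undo entry into the sample that depends on the outcome itself.

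At stake are the infection, stay and return comparisons, where the groups may differ modestly and a few control patients can move the result. A fixed number also discards any further eligible controls, who would add precision without new enrolment.

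**Working it through.** **1. The plan's own figure.** Section 6.1 claims more than 90% power at two-sided 0.05. With 20 v 100, power is about 1.00 at 90% v 10% closed and still 0.93 at 70% v 30%. With 20 v 20 it is about 1.00 at 90% v 10%. The claim therefore reproduces under the anticipated rates with either control number. It does not depend on how controls are selected.

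**2. Primary outcome.** Suppose selection went badly against the expectation: 18/20 closed with tertiary closure and 8/20 in the controls (assumed). For a 2×2 table with rows (a, b) and (c, d) and total N, chi-squared = N(ad − bc)² / (product of the four margins). Here it is 40 × (18×12 − 2×8)² / (20×20×26×14) = 10.99, p = 0.0009. The primary conclusion is robust to a large shift.

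**3. Infection: inputs.**
- Tertiary group of 20 and control target of 20: sections 6.1 and 2.1.1.
- Assumed: 40 eligible controls, 8 infected (20%). Section 1.0 gives 20–25% for contaminated wounds. The pool size is not in the documents.
- Assumed: 2/20 infected in the tertiary group.

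**4. What a set of 20 can contain.** There are 32 uninfected patients, so a set of 20 can hold anything from 0 to 8 infections (0–40%). For a random draw, Hypergeometric(40, 8, 20) gives 2 to 6 (10–30%) as the 95% range. Drawing all 8 at random has probability 0.0016.

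**5. Resulting tests (uncorrected chi-squared).**

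| Controls infected | Chi-squared | p |
|---|---|---|
| 2/20 | 0 | 1.00 |
| 6/20 | 40×(2×14 − 18×6)²/(20×20×8×32) = 2.50 | 0.11 |
| 7/20 | 40×(2×13 − 18×7)²/(20×20×9×31) = 3.58 | 0.058 |
| 8/20 | 40×(2×12 − 18×8)²/(20×20×10×30) = 4.80 | 0.029 |
| 8/40 (all) | 60×(2×32 − 18×8)²/(20×40×10×50) = 0.96 | 0.33 |

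At 8/20, Fisher's exact test gives p = 0.065 and the continuity-corrected chi-squared 0.068.

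**6. Precision.** The standard error of the difference at 10% v 20% is √(0.1×0.9/20 + 0.2×0.8/20) = 0.112 with 20 controls and √(0.1×0.9/20 + 0.2×0.8/40) = 0.092 with all 40, about 18% smaller.

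**7. Range over pool size and target.**
- Pool 20, target 20: no choice, no effect.
- Pool 40, target 100: all 40 are taken, no choice.
- Pool 150 with 45 infected, target 100: 0 to 45 infections are possible. Against 4/20 in the tertiary group, p runs from below 0.001 favouring secondary closure to 0.038 favouring tertiary closure.

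**8. Partial rather than extreme selection.** Assume 25% infected in both groups, a target of 20, and infected charts with higher odds of being picked. The chance of a falsely significant tertiary benefit on infection is:

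| Eligible pool | Random | Odds ×2 | Odds ×3 |
|---|---|---|---|
| 40 | 1.3% | 5.8% | 12.4% |
| 60 | 1.7% | 10.0% | 22.1% |
| 100 | 2.0% | 13.3% | 28.8% |

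Stay and return are not quantified, because the documents give no control figures for them. The mechanism is the same.

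**The case against.** The strongest reply is that the plan is silent here and does not describe a faulty practice. It gives eligibility, type of closure, year and number. It does not say who chooses, that postoperative notes are read first, or that review stops at a count. A reader might infer that controls will be picked by outcome; the text does not support that. What stands is that no rule excludes it.

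A reader might also infer that a control needs a clinic note showing closure, so that patients who died, stayed in hospital or were followed elsewhere drop out. Section 2.1.1 says only that closure can be read from those notes. It does not make a note a condition of entry, and it does not cover the other outcomes.

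The pool may be no larger than the target. Section 6.5 expects twenty tertiary patients in a year. That is accrual and not eligible volume, but it is compatible with about 20 eligible patients in 2018. The 100 in section 6.1 points the other way, though that section names no year. Which number holds decides whether there is anything to choose, so the concern does not apply at every control count.

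Finally, in the 40-chart example significance appears only when every infected chart is taken, and only with the uncorrected test. That objection stands against reading the example as a typical result. It does not answer the table in step 8, where moderate preference is enough to inflate false positives. These are secondary comparisons in a small cohort, which limits the consequence.

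**Conclusion.** The concern holds as a gap in control selection, worth closing before charts are read. It is not a finding that selection is biased. It rests on one condition the documents leave open: that eligible patients outnumber the target, itself stated as both 20 and 100. If every eligible patient is taken, the problem disappears. Where there is a surplus, the control infection proportion can range widely from the same pool (0–40% in the 40-chart illustration, against a true 20%), and baseline adjustment offers no protection. The primary closure result is unlikely to be affected at the anticipated rates. It would go too far to say that significance on infection generally turns on the pick: in the 40-chart example this needs the extreme 8/20, and that result is lost under Fisher's exact test.

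**What to change.** In section 2.1.1, replace the fixed count with a procedure, and align section 6.1 so that one control number or rule applies throughout:

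- List all laparotomies in the control period from the operating-room log, in date order.
- Decide eligibility from the operative and anaesthesia records only.
- Freeze the list before any postoperative note is opened.
- Analyse every eligible patient. If a fixed number is kept, take consecutive patients by date.
- Do not drop a listed control because no clinic note shows closure. Keep that patient in the infection, stay and return analyses as far as the record allows, and show the closure result with that patient counted as closed and as not closed.

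The cost is a log extract and possibly more charts to read, with no new patients, visits or procedures. The control results may become less favourable to tertiary closure. If the intention was always to take every eligible patient, stating that together with the frozen list settles the point.

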2.2 Secondary Objective

2.2.1 To compare the proportion of acute and chronic wound infection in wounds closed with a tertiary closure technique to historical controls receiving a secondary wound closure.

- 2.2.2 To compare the length of stay of patients receiving a tertiary wound closure to historical controls receiving a secondary wound closure.
- 2.2.3 To describe the number of patients receiving a tertiary wound closure that return within 30 days of surgery as compared to historical controls receiving a secondary wound closure.
- 2.2.4 To describe the quality of life in patients receiving a tertiary wound closure.

3.0 Study Population

3.1 Inclusion Criteria

- 3.1.1 Patients with high risk class II, class III, class IV abdominal wounds
- 3.1.2 Undergoing laparotomy for gynecologic related disorders

Patients undergoing laparotomy for both benign and malignant diagnoses will be included in this study

3.2 Exclusion Criteria

- 3.2.1 Pregnancy
- 3.2.2 Allergy to triclosan
- 3.2.3 Patients undergoing HIPEC

3.3 Inclusion of Women and minorities

- 3.3.1 Women of all races and ethnicity who meet the above-described eligibility criteria are eligible for this trial.
- 3.3.2 The study consent form will also be provided in Spanish for Spanish-speaking participants. Based on WFBCCC population estimates, we expect approximately 25% Black or African American (N=5) and 10% of individuals to be combination of American Indian/Alaska Native, Asian and Hispanic/Latina ancestry. Should we not meet or exceed these estimates, the PI will engage the Cancer Center Health Equity Advisory Group to discuss strategies to enhance recruitment in these target populations.

4.0 Methods

4.1 Registration Procedures

All patients entered on any WFBCCC trial, whether treatment, companion, or cancer control trial, **must** be linked with a study protocol in EPIC within 24 hours of Informed Consent. Patients **must** be registered prior to the initiation of the study.

You must perform the following steps in order to ensure prompt registration of your patient:

- 1.0 Complete the Eligibility Checklist ([Appendix A](#))
- 2.0 Complete the Protocol Registration Form ([Appendix B](#))
- 3.0 Alert the Cancer Center registrar by phone, *and then* send the signed Informed Consent Form, Eligibility Checklist and Protocol Registration Form to the registrar, either by fax or e-mail.

Contact Information:

Protocol Registrar [contact]

Protocol Registrar [contact]

Protocol Registrar E-MAIL ([contact])

*Protocol Registration is open from 8:30 AM - 4:00 PM, Monday-Friday.

- 4.0 Fax/e-mail ALL eligibility source documents with registration. Patients **will not** be registered without all required supporting documents.

Note: If labs were performed at an outside institution, provide a printout of the results. Ensure that the most recent lab values are sent.

To complete the registration process, the Registrar will:

- assign a patient study number
- register the patient on the study

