4.2 Study Activities Table

	Pre-Study	At Surgery	2 weeks post-surgery (+/- 5 days)	4 weeks post-surgery (+/- 5 days)	3-month Follow-up (+/- 5 days)
Informed consent	X				
Demographics	X				
Medical history					
• Surgical History	X				
Concurrent meds	X				
Physical exam	X				X
Vital signs	X				X
Wound Characteristics					
• Wound Class		X			
• Wound Depth					
• Wound Size					
Duration of Surgery	X	X			
Wound Assessment			X	X	X
Quality of life (SF-36)	X		X	X	X
CBC w/diff, platelets	X				
Comprehensive Metabolic Panel	X				
B-HCG (urine or serum)	X				
Adverse event evaluation		X	X	X	X

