6.4 Analysis of Secondary Outcomes

6.4.1 The analysis approach for comparing the proportion of acute and chronic wound infection between the two groups is the same as that specified in 6.3.

6.4.2 The distribution of length of stay will be examined and transformed if needed. To compare the length of stay between the two groups, the 2-sample t-test will be used if the length of stay is normally distributed and the Wilcoxon rank sum test will be used if it is not normally distributed. To adjust for confounding variables, a linear regression model will be used if the length of stay is normally distributed and a negative binomial model will be used if it is not normally distributed.

6.4.3 The analysis approach for comparing the proportion of patients that return within 30 days of surgery between the two groups is the same as that specified in 6.3.

6.4.4 Descriptive statistics, including mean, standard deviation, median, and interquartile range, will be calculated to describe the quality of life in patients receiving a tertiary wound closure,

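### Consent, paperwork and weekday registration apply only to tertiary patients, so urgent class IV cases may be under-enrolled relative to the 2018 controls, favouring tertiary closure on infection

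*Combined protocol and SAP*

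**What the plan says.** **Tertiary group.** Section 4.1 says patients must "be registered prior to the initiation of the study". Staff must first "send the signed Informed Consent Form, Eligibility Checklist and Protocol Registration Form to the registrar" and "Fax/e-mail ALL eligibility source documents with registration"; without the supporting documents no registration takes place. On hours, "Protocol Registration is open from 8:30 AM - 4:00 PM, Monday-Friday". No out-of-hours route is described. The table in Section 4.2 puts consent, SF-36, blood count, "Comprehensive Metabolic Panel" and pregnancy test in the pre-study column. Under Section 4.3.3 the technique begins in theatre, with the untightened skin suture and the vacuum device, so these steps have to come before the operation.

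**Controls.** Section 2.1.1 takes patients with the inclusion characteristics "who underwent laparotomy with secondary wound closure during the calendar year 2018", found from charts. It sets no condition on consent, hours or urgency.

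**Risk by wound class.** Section 1.0 states: "A perforated viscus or abscess requiring surgery would be considered a dirty/infected or class IV wound". Its table gives infection rates of 5-6% for class II, 20-25% for class III and 30-40% for class IV. All three classes are eligible (Section 3.1), class II only if high risk.

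**Analysis.** Section 6.3 uses a chi-squared test, with logistic regression for confounders; age is the only example named. Section 6.4.1 says: "The analysis approach for comparing the proportion of acute and chronic wound infection between the two groups is the same" as in 6.3. Return within 30 days is handled in the same way, and length of stay may be adjusted for unnamed confounders.

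**Forms.** Appendix E records wound class, date of surgery and start and stop times. Neither Appendix D nor Appendix E has a scheduled/urgent item.

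**The concern.** The two groups pass through different filters. A weekend laparotomy for an abscess in 2018 can serve as a control if the wound was left open. The same patient during the trial could be registered before surgery only if the operation waited for office hours. If such patients enrol less often, the controls hold more high-risk wounds for a reason unrelated to how the wound was closed.

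Infection would then look better after tertiary closure even if the technique had no effect. Length of stay and return would plausibly move the same way. The plan neither records urgency nor names urgency or wound class for adjustment, so a reader of the results could not separate technique from case selection. Adjusting for wound class alone would still leave any difference between urgent and scheduled cases within a class.

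**Working it through.** **1. The plan's own figure.** Section 6.1 claims more than 90% power for 30-day closure. A two-proportion calculation with pooled variance, two-sided 0.05, 20 tertiary patients and 100 controls gives 99.99% at 80% v 20% and 93% at 70% v 30%. With the 20 controls of Section 2.1.1 it gives 98.9% and 73%. The claim holds for the anticipated rates near 100% v 0%, and a case-mix shift is a minor matter for a contrast of that size. The check below therefore concerns infection.

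**2. Registration hours.** 5 days x 7.5 h = 37.5 h; 37.5/168 = 22.3% of the week. This is used as a relative enrolment rate r = 0.22. It would be correct only if urgent cases arrive evenly over the week and cannot wait. r = 0 means none enrol; r = 1 means no filter.

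**3. Infection rates.** Midpoints of the Section 1.0 ranges: class II 5.5%, class III 22.5%, class IV 35%. No treatment effect is assumed.

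**4. Case mix (assumed; the documents give none).** Control mixes II/III/IV of 50/20/30, 40/25/35 and 20/30/50. The entry conditions are taken to act on class IV only: multiply the class IV share by r and rescale to 100%, which keeps the ratio of class II to class III.

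Example, controls 40/25/35:
- Control infection = 0.40 x 0.055 + 0.25 x 0.225 + 0.35 x 0.35 = 20.1%.
- With r = 0 the tertiary mix is 40/65 = 61.5% and 25/65 = 38.5%, so infection = 0.615 x 0.055 + 0.385 x 0.225 = 12.0%.
- With r = 0.22, class IV becomes 0.35 x 0.22 = 0.077 and the total 0.727. The mix is 55.0/34.4/10.6 and infection 14.5%.

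**5. Chance of a falsely significant result favouring tertiary closure.** Exact enumeration of two binomials, uncorrected chi-squared at two-sided 0.05, 20 tertiary patients. Sections 2.1.1 and 6.1 disagree on the number of controls (20 and 100), so both are shown.

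| Control mix | r | Infection, tertiary v control | 20 controls | 100 controls |
|---|---|---|---|---|
| 50/20/30 | 1 | 17.75% v 17.75% | 2.5% | 1.6% |
| | 0.22 | 12.5% v 17.75% | 6.5% | 5.2% |
| | 0 | 10.4% v 17.75% | 9.4% | 8.1% |
| 40/25/35 | 1 | 20.1% v 20.1% | 2.5% | 1.7% |
| | 0.22 | 14.5% v 20.1% | 6.6% | 5.7% |
| | 0 | 12.0% v 20.1% | 9.9% | 9.2% |
| 20/30/50 | 1 | 25.35% v 25.35% | 2.6% | 2.0% |
| | 0.22 | 19.2% v 25.35% | 6.7% | 6.5% |
| | 0 | 15.7% v 25.35% | 11.2% | 12.0% |

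**6. Sensitivity.** A simpler model has an urgent share u at 35% infection and all other wounds in one class. The tertiary urgent share is u x r/(u x r + 1 - u).
- Others all class II, u = 10-20%, r = 0.22 or 0: 0.1-1.9% with 100 controls, 2.5-6.8% with 20.
- Others all class II, u = one third to one half: about 6-12% at r = 0.22 and 12-32% at r = 0.
- Others all class III, same u: about 4-5% at r = 0.22 and 5-7% at r = 0. Here the infection gap at r = 0.22 is 0.9 points at u = 10%, rising to 4.0 at u = 50%.

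The direction is the same whenever r < 1 and urgent cases carry more risk. Stay and return cannot be sized, because the documents give no rates by class or urgency.

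**The case against.** The strongest reply is that nothing shows the imbalance exists. No section gives an urgent share or class mix for either group. Class IV is expressly eligible. An abscess need not be operated on out of hours, some urgent cases arrive in hours or can wait, and the pre-study blood tests are quick. All of this stands, and it is why the point says only that the trial group may under-enrol these cases. The six-patient series in Section 1.0 included two class IV abscesses, so such patients do occur in this practice. The protocol describes its submitted series as a chart review (Section 5.2.4, which counts five patients), so it does not show that they would meet the trial's entry conditions.

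A second reply is that the plan can already adjust: wound class is on Appendix E, the confounder list is open, and date and start time would identify out-of-hours surgery in tertiary patients. That is partly right. But neither variable is pre-specified, no matching abstraction is specified for the controls, time of day is only a proxy for urgency, and adjustment with 20 tertiary patients is weak.

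A reader might infer a much larger effect. Setting tertiary patients at 80/15/5 against controls at 40/25/35 gives 9.5% v 20.1% infection and a false-result chance of 15%; 90/10/0 against 20/30/50 gives 35-44%. The arithmetic is correct, but removing every class IV case from those control mixes yields 61.5/38.5/0 and 40/60/0. The rest is a class II/III shift that registration hours do not explain: gastrointestinal spillage, for instance, arises during surgery.

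**Conclusion.** The asymmetry is in the text: the entry conditions apply to one group only, urgency is not recorded, and neither urgency nor wound class is named for adjustment. If urgent class IV cases are under-enrolled, the infection comparison leans towards tertiary closure. On the class-mix assumptions in step 4, the false-result chance rises from about 2-2.5% to about 5-7% (r = 0.22) or 8-12% (r = 0). It is under 2% with a 10-20% urgent share and 100 controls, and step 6 shows how far it depends on the class of the remaining wounds. The effect on stay and return is plausible in direction only.

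The documents do not support the stronger statement that urgent abscess and perforation cases fall mainly in the control group, nor that the sickest patients hardly ever enter the trial. The consequence is confined to secondary comparisons in an openly non-randomised study. It still deserves a change, because the urgent share is unknown and the plan as written would leave it unknown.

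**What to change.** - **Appendix E:** add one item, scheduled or urgent/emergency. Abstract the same item, with wound class, for every control.
- **Section 2.1.1:** select the 2018 controls to match the urgency and wound-class mix of the enrolled tertiary patients. If no urgent patients enrol, use scheduled 2018 laparotomies only. Excluding urgent controls from the outset is not advised: if urgent patients do enrol, they would have no comparators and the bias could reverse.
- **Sections 6.3 and 6.4:** name urgency and wound class as the adjustment or stratification variables for infection, length of stay and return.

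**Cost:** one more item to complete and abstract, and possibly fewer usable 2018 controls. Precision of any adjustment will be limited with 20 tertiary patients, so the results by urgency and class should also be shown descriptively. The control count (20 or 100) needs to be reconciled at the same time, since it determines how much matching is possible.
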